**A Mechanistic Perspective on Post-Activation Performance
Enhancement Responsiveness: A Randomized Controlled
Study of Acute Changes in Muscle Architecture, Contractile
Property Kinetics, and Muscle Excitability**

NCT06982937

18.05.2025

Objectives and endpoints.

The primary objective is to test whether a heavy conditioning activity (CA; one set of 2–3 repetitions at ~90% 1RM) produces post-activation performance enhancement (PAPE) in countermovement jump (CMJ) height compared with a control treadmill warm-up within the 4–12 min window after the intervention. The analysis does not assume *a priori* when the maximal effect occurs; instead, the minute of maximal between-group difference (denoted T^*) will be identified empirically. The primary endpoint is the change in CMJ height from baseline (ΔCMJ) at post-intervention time points (4, 6, 8, 10, 12 min). Secondary endpoints include the time-course of ΔCMJ within the experimental group (EXP), individual responder status at each time point, and the associations between neuromuscular phenotype—estimated as %MHC-I from tensiomyography (TMG)—and the magnitude, timing, and likelihood of response. Ultrasound (USG) morphology (muscle thickness, pennation angle, derived fascicle length) will be analysed in parallel to performance endpoints. Electromyography (EMG), where available, will be treated analogously to USG/TMG (see below).

Data handling and derived variables.

At each time point, CMJ height is the mean of three trials; ΔCMJ and percentage change (% ΔCMJ) will be computed relative to baseline. Individual response is classified using MDC. USG outcomes will be averaged across three images; fascicle length is calculated as thickness divided by the sine of pennation angle (degrees converted to radians). TMG-based %MHC-I is estimated from delay, contraction, and half-relaxation times using the published multivariable model; TMG amplitudes and time constants may also be expressed as Δ or % Δ . If EMG is collected, signals will be band-pass filtered, rectified, quantified with 50-ms RMS, normalized (to MVC or M-wave), and summarized over task-relevant phases; % Δ at 4–12 min is computed analogously. Values >3.5 SD from group-time means will be flagged; primary analyses include all data, with winsorized sensitivity checks reported only if inferences change. Missing data will be not imputed for the primary analysis; mixed-effects models accommodate missingness assuming MAR.

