Primary analysis and identification of the peak time (T^*).

The confirmatory analysis uses a RM-ANOVA with ΔCMJ as the outcome, Group (EXP vs CON), Time (time effect: 4, 6, 8, 10, 12 min), and Group \times Time. If the interaction is significant, we estimate adjusted between-group contrasts at each minute with Bonferroni correction across the five time points. T^* is defined as the minute showing the largest positive EXP–CON difference in estimated marginal means (EMMs) with the smallest p-value. We report the EMM difference at T^* (95% CI) and effect size (d’Cohen). Greenhouse–Geisser correction if needed.

Within-group time-course and kinetics.

To describe the temporal profile without prespecifying a target minute, we analyse ΔCMJ across time within EXP using a one-way repeated-measures ANOVA (or LMM if assumptions are violated), followed by Bonferroni-adjusted pairwise EMMs to locate the within-group peak. To characterise response timing at the individual level, we model time to first and time to peak response (4–12 min) using Kaplan–Meier curves with censoring at 12 min, compare strata by log-rank tests, and fit Cox proportional-hazards models to estimate hazard ratios (HR, 95% CI) and concordance (C-index). This kinetics framework provides an assumption-light estimate of when athletes typically express PAPE.

Responder analyses and discrimination.

Responder distributions (Positive/neutral/adverse) will be compared between EXP and CON at each minute using likelihood χ^2 test. For mechanistic discrimination at specific minutes (including T^* once identified), we fit logistic models with %MHC-I as a continuous predictor and report ORs (95% CI),

Nagelkerke R², AIC, Hosmer–Lemeshow calibration, and ROC-AUC with sensitivity, specificity, and Youden's J cut-offs. Moderation analysis also will be used with simple slope analysis.

Phenotype and morphology linkages (USG/TMG/EMG).

Associations between %MHC-I and Δ CMJ will be quantified at each minute using Pearson's r. USG variables (thickness, pennation angle, fascicle length) will be analysed with the same three lenses applied to performance: (i) within-EXP time-course (rmANOVA/LMM with Tukey), (ii) responder linkage at each minute (one-way ANOVA or robust alternative; Hedges' g for P vs X), and (iii) phenotype linkage (correlations and moderation models). TMG (e.g., Dm, Tc, Tr) and EMG (e.g., normalized RMS, median frequency) follow this identical framework to ensure coherence across modalities.

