Moderation and mediation (pre-specified).

All moderators and predictors will be mean-centered; multicollinearity is checked (VIF < 5). Primary moderation models test whether (a) baseline CMJ modifies the effect of %MHC-I on Δ CMJ and (b) baseline morphology (thickness, pennation angle, fascicle length) modifies the effect of baseline CMJ on Δ CMJ. Significant interactions will be decomposed with simple slopes at -1 SD, mean, and +1 SD, with 95% CIs via nonparametric bootstrap (1,000 resamples) and publication-ready interaction plots. Exploratory mediation tests whether acute morphological change (e.g., % Δ thickness at a given minute) transmits baseline morphology effects to % Δ CMJ; indirect, direct, and total effects will be estimated by bootstrap (5,000 resamples; bias-corrected CIs) and interpreted cautiously.

Assumptions, multiplicity, and robustness.

Model diagnostics include residual normality (Shapiro–Wilk), homoscedasticity (residual–fitted patterns, Breusch–Pagan), linearity, and independence by design. Sphericity is tested for rmANOVA (Mauchly) with Greenhouse–Geisser corrections as needed. If mechanistic variables are skewed, appropriate transformations (e.g., log for EMG amplitude) are considered; otherwise we rely on LMM robustness. Multiplicity is controlled via Holm across the five between-group contrasts, FDR for correlation families, and restraint in post-hoc testing; moderation/mediation will be estimation-focused with full interval reporting and are not used to redefine the primary inference.

Reporting, visualization, and software.

We report means \pm SD with 95% CIs; between-group effects as Hedges' g; within-subject effects as d_{nZ} ; ANOVA-style effects as η^2 ; logistic results as ORs with AUC; and survival results as HRs with concordance. Figures include EMM trajectories with 95% CIs, individual waterfall plots with MDC bands, ROC curves for %MHC-I, Kaplan–Meier curves for first/peak response, interaction plots for significant moderations, and path diagrams for supported mediations. Analyses will be performed in Jamovi 2.6 and STATISTICA 13.1.

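### Moderation is described as estimation-focused, but significance with no named multiplicity method decides which interactions are decomposed and plotted

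*Combined protocol and SAP*

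**What the plan says.** Under Moderation and mediation (pre-specified), the primary moderation models ask two things. Model (a) asks whether "baseline CMJ modifies the effect of %MHC-I on Δ CMJ". Models (b) ask whether "baseline morphology (thickness, pennation angle, fascicle length) modifies the effect of baseline CMJ on Δ CMJ". That is one interaction plus three. The next sentence sets the display rule: "Significant interactions will be decomposed with simple slopes", with bootstrap confidence intervals and plots attached to that decomposition. The figure list under Reporting, visualization, and software repeats the rule: "interaction plots for significant moderations, and path diagrams for supported mediations".

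Under Assumptions, multiplicity, and robustness, Holm is assigned to the five between-group contrasts and FDR to families of correlations, with a general call for restraint in post-hoc work. For this part of the plan the same sentence says that "moderation/mediation will be estimation-focused with full interval reporting" and adds that these analyses will not alter the primary inference. No adjustment is named for moderation.

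The outcome is measured at "post-intervention time points (4, 6, 8, 10, 12 min"). The primary moderation models name no time point. Phenotype and morphology linkages also lists "phenotype linkage (correlations and moderation models") for ultrasound and extends the same framework to TMG and EMG. Responder analyses and discrimination mentions moderation with simple slopes once more, without a count.

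**The concern.** An estimation approach reports every prespecified estimate with its interval and lets the reader judge. Here the p-value selects which interactions are broken down, given bootstrap intervals and drawn. The label and the display rule pull in opposite directions.

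The selection uses an unadjusted threshold over a family whose size is not fixed. With no time point stated, the analyst could fit one, several or all five and make that choice after seeing the data. Interactions that pass such a filter in a small study include chance findings, and their estimates tend to be too large because they were selected for being large. Mechanism is in the study's title and these models are called primary and prespecified, so readers are likely to give the plotted interactions weight.

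**Working it through.** The documents give no alpha, sample size or error rate for moderation, so there is no stated figure to reproduce.

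**Inputs from the plan**
- Interactions: 1 (baseline CMJ × %MHC-I) + 3 (baseline CMJ × thickness, × pennation angle, × fascicle length) = 4.
- Post-intervention time points: 5.
- Fascicle length is computed as thickness over the sine of pennation angle, so the three morphology tests are dependent.

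**Assumptions**
- Two-sided alpha of 0.05 per interaction and no true moderation.
- n = 20 or 40.
- Correlation of ΔCMJ between time points from 0 to 0.9.
- Means and SDs for thickness and pennation angle.

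**Count.** One time point gives 4 tests; all five give 4 × 5 = 20. The expected number of false significant interactions is 4 × 0.05 = 0.2 or 20 × 0.05 = 1.0, whatever the correlation.

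**Independent tests, for reference.** P(at least one) = 1 − (1 − 0.05)^k.
- k = 4: 1 − 0.95^4 = 18.5%
- k = 20: 1 − 0.95^20 = 64.2%

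**Dependent tests, by simulation.** Each of the four models was fitted by least squares with centred predictors at all five time points, 4,000 null data sets per setting. The Monte Carlo standard error is at most √(0.25/4000) = 0.8 percentage points.

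| Between-minute correlation | Any of 20, n = 20 | Any of 20, n = 40 | FDR over 20, n = 20 | FDR over 20, n = 40 |
|---|---|---|---|---|
| 0 | 58.5% | 57.6% | 4.6% | 4.9% |
| 0.3 | 54.6% | 54.3% | 4.5% | 4.3% |
| 0.5 | 49.8% | 48.3% | 5.3% | 4.7% |
| 0.7 | 41.8% | 41.3% | 3.6% | 4.2% |
| 0.8 | 36.5% | 36.8% | 3.7% | 3.7% |
| 0.9 | 30.0% | 30.3% | 3.6% | 2.8% |

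Four tests at a single time point gave 14.9–16.5% unadjusted across all settings. Four tests on the five-minute average gave about 15–17% unadjusted and 4–5% with FDR.

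The upper rows of the table are the less plausible ones. ΔCMJ at the five time points comes from the same athletes and subtracts the same baseline, so moderate to high correlation is expected. The documents give no value, and 0.5 to 0.9 is an assumed range.

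**The case against.** The strongest reply is that these analyses are secondary and fenced off: the plan promises full intervals and says that moderation will not alter the primary inference. Probing simple slopes only after a significant interaction is also common practice. The fencing stands, so the confirmatory EXP–CON comparison is not affected. The promise of intervals helps only in part, because the simple slopes, their bootstrap intervals and the plots are tied to significance in two separate places.

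A reader might infer four stronger things that the documents do not support.

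- **That 20 tests are planned.** The text names four interactions. Where it wants analysis by minute it says so, as in "Associations between %MHC-I and Δ CMJ will be quantified at each minute using Pearson's r"; it does not say so for the primary moderation models. Nor is 20 a ceiling, given the further USG, TMG and EMG models. The actual gap is that time points and model count are unstated.
- **That a false moderation will probably be shown.** A chance above one half needs all five time points and weak correlation between them. For the four named interactions it is about one in six.
- **That non-significant interactions will go unreported.** Significance governs the decomposition and the figures. Full interval reporting can fairly be read as covering every interaction estimate.
- **That 0.05 is the plan's threshold.** No alpha is given; it is an assumption here.

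A further objection concerns the remedy. Replacing minute-specific models by one pooled test per moderator would dilute moderation confined to a few minutes, in a study whose secondary endpoints include the timing of response. That objection stands, and the fix allows for it.

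**Conclusion.** The concern holds in a limited form. The display rule contradicts the estimation-focused description, and no named method controls the tests that drive it. Assuming alpha 0.05, n of 20 to 40 and no true moderation, at least one false interaction would pass in about 15–17% of trials with four tests. With 20 tests the figure is about 30–50% at between-minute correlations of 0.5 to 0.9. If some moderation is real, the chance of a false one changes with the number of true nulls left.

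The consequence is selective display among secondary mechanistic findings, not an error in the primary result. This is a worthwhile, low-cost improvement rather than a serious flaw.

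**What to change.** 1. In Moderation and mediation, and in the figure list, remove significance as the condition for display. Report the interaction estimate, 95% CI, simple slopes and plot for all four primary moderation models.
2. State the time point(s) at which these models are fitted, and the alpha.
3. Where an interaction is called significant, apply FDR across all primary interaction tests actually run, 4 or 20. The plan now reserves FDR for correlations, so this is an extension of it. With no true moderation, the chance of any false call falls to about 4–5% for 4 tests and 3–5% for 20.
4. A single model over all five time points may be added as a summary, but should not replace the minute-specific estimates.

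Step 1 removes the display selection by itself; step 3 matters only for the use of the word significant. The cost is a few more supplementary figures and fewer interactions called significant. No new data or participants are needed.

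### No named multiplicity procedure covers the 30 to 40 or more ANOVAs that link ultrasound, TMG and EMG variables to responder class, although the SAP says multiplicity is controlled

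*Combined protocol and SAP*

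**What the plan says.** The tests are set out in *Phenotype and morphology linkages (USG/TMG/EMG)*: "USG variables (thickness, pennation angle, fascicle length) will be analysed with the same three lenses applied to performance". The second of these lenses is "responder linkage at each minute (one-way ANOVA or robust alternative", accompanied by a Hedges' g between two of the classes. The other modalities are then brought in: "TMG (e.g., Dm, Tc, Tr) and EMG (e.g., normalized RMS, median frequency) follow this identical framework to ensure coherence across modalities".

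*Objectives and endpoints* gives the times, "post-intervention time points (4, 6, 8, 10, 12 min", and makes one modality conditional: "Electromyography (EMG), where available, will be treated analogously to USG/TMG". The responder classes come from *Responder analyses and discrimination*: "Responder distributions (Positive/neutral/adverse) will be compared between EXP and CON at each minute".

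The multiplicity statement is in *Assumptions, multiplicity, and robustness*. It says that multiplicity is controlled and names Holm for the five between-group contrasts, followed by "FDR for correlation families, and restraint in post-hoc testing". It adds that moderation and mediation are estimation-focused and will not redefine the primary inference.

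**The concern.** A reader of the multiplicity paragraph would take it to cover the planned tests. It does not cover lens (ii): those are ANOVAs, not correlations, and they are not the five jump-height contrasts. They are also planned omnibus tests, so a remark about post-hoc testing does not apply to them; in any case restraint has no threshold, family or decision rule. The plan is uneven as a result. The correlations under lens (iii) get FDR, while the ANOVAs on the same variables under lens (ii) get nothing.

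The study's title promises a mechanistic account of responsiveness, and lens (ii) is one of the places where muscle architecture, contractile properties and excitability are tied to being a responder. A chance finding at a single minute would read as a time-specific mechanism.

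**Working it through.** The documents give no test count, significance level, sample size or error rate for this family, so there is no stated figure to reproduce.

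**Step 1. Which control reaches lens (ii)?**

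| Control in the SAP | What it covers | Reaches lens (ii)? |
|---|---|---|
| Holm | Five EXP–CON contrasts in jump height | No |
| FDR | Correlation families | No; lens (ii) uses ANOVA |
| Restraint | Post-hoc tests, no rule given | No |
| Tukey | Lens (i), time-course within EXP | No |
| Exploratory or estimation-focused label | Mediation and moderation | No |

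**Step 2. Count.** Named variables: 3 ultrasound, 3 TMG, 2 EMG. Minutes: 5.

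- With EMG: (3 + 3 + 2) × 5 = 40.
- Without EMG: (3 + 3) × 5 = 30.
- Ultrasound alone, the only closed list: 3 × 5 = 15.

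**Step 3. Expected false positives** with no true links: m × α. I assume α = 0.05.

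- 40 × 0.05 = 2.0; 30 × 0.05 = 1.5; 15 × 0.05 = 0.75.

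An expectation is a sum over tests, so correlation between tests does not change these figures.

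**Step 4. Chance of at least one, independent tests:** 1 − (1 − α)^m.

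- 1 − 0.95^40 = 87.1%; 1 − 0.95^30 = 78.5%; 1 − 0.95^15 = 53.7%.
- If α were 0.01: 1 − 0.99^40 = 33.1%.

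**Step 5. Allow for dependence.** The tests cannot all be independent. Under *Data handling and derived variables*, fascicle length is computed from thickness and pennation angle, and the same participants are measured every two minutes. I used a simulation with no true links: three responder classes, five minutes, 1,500 runs per setting. The sample size (20 or 40) and all correlations are assumptions. The Monte Carlo standard error is about 1 point, for example √(0.82 × 0.18 / 1,500) = 0.010.

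| Assumed correlation (across minutes; between variables) | 40 tests | 30 tests |
|---|---|---|
| Moderate (0.5–0.7; 0.3) | about 82% | 73–75% |
| Strong (0.8–0.9; 0.5) | 65–75% | 59–66% |
| Extreme (0.95; 0.8) | 40–43% | 36–38% |

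The mean number of false positives stayed near 2.0 and 1.5 throughout.

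**Step 6. After a correction.** With Benjamini–Hochberg over all 40 tests as one family, the simulated chance of any false link was about 3–6% across these settings. With a separate family for each modality there are three families, and under independence the chance is 1 − 0.95^3 = 14%. A second simulation (3,000 runs per setting; assumed n of 15 or 30, minute correlation 0.5–0.9, between-variable correlation 0–0.5) gave 12–15% per modality, against 4.5–5.7% for one family.

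**The case against.** The strongest reply is that these tests carry little inferential weight. Only the RM-ANOVA of jump height is called confirmatory. The responder ANOVAs are not among the listed secondary endpoints, and ultrasound is merely analysed in parallel. The plan also promises effect sizes and 95% CIs, which do not depend on a significance threshold.

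Part of this stands: the primary inference is untouched, and the gap concerns mechanistic analyses only. It does not close the gap, because the SAP says without qualification that multiplicity is controlled and never labels the lens (ii) tests exploratory. That label, together with a commitment to make no significance claims, would be an adequate answer, but the plan does not contain it.

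A second reply concerns size, and it is right. A reader might infer that at least one false mechanistic link is close to certain, on the strength of the 87% figure. The documents do not support that. The figure needs 40 tests, a 5% level, independence and no true link anywhere. No level is stated, EMG is conditional, and at least one variable is derived from two others. In the other direction, the TMG and EMG lists are examples only. TMG measures may also be expressed as changes, and EMG is summarised over several task phases, so the count could exceed 40.

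**Conclusion.** The concern holds as a gap in coverage: no named procedure applies to the lens (ii) ANOVAs, and their family is not defined. With the named variables there are 40 tests (30 without EMG, possibly more than 40). At an assumed 5% level with no true links, about 2.0 (or 1.5) false positives are expected. The chance of at least one among 40 is 87% under independence, roughly 65–82% under moderate to strong correlation and about 40% under extreme correlation. The expected count is the firmer figure because it does not depend on correlation; the probabilities rest on correlations and sample sizes that the documents do not give.

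The plan should be changed, but the gap does not threaten the trial's main conclusion.

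**What to change.** List the lens (ii) variables by modality. Then add to the multiplicity paragraph:

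> *BH-FDR at 5% is applied across all lens (ii) omnibus tests (all variables × five minutes) as one family, as for correlations; all P v X Hedges' g values are reported with 95% CIs, but a responder link is claimed only where the FDR-adjusted omnibus test is significant.*

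- **One family.** This holds the chance of any false link to about 5% when no links exist. If the sponsor prefers one family per modality, the SAP should say that the corresponding figure is about 14%.
- **Report every effect size.** Showing g only after a significant omnibus test would select inflated estimates and would cut against the plan's own interval reporting.
- **Restraint.** The phrase may stay as a description of post-hoc practice, but it should not be presented as the control for these tests.

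The cost is SAP wording, with no new data, and fewer nominally significant mechanistic results.
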